- Have contraindication to NRT (past month myocardial infarction, history of serious arrhythmias/or unstable angina pectoris, dermatological disorder),⁶³
- Currently being treated for a psychiatric condition.
- Currently being treated for smoking cessation, alcoholism, or illicit drug use

5) Procedures Involved*

Aim 1: The Clinical Trial

We will be provided with a list of potentially eligible participants including their names, contact information, smoking status, most recent HIV-1 viral load (VL), CD4 count, ART regimen history (e.g., time since first starting ART, current prescription) from the UM HIV Registry (pls. see LOS from [name]; their IRB # is pending approval of this protocol). This will include HIV Registry participants who have previously given consent to be contacted for future research studies. Eligible participants will be contacted by phone and invited to participate in the study. Those who are interested will be screened. Those who are eligible will be scheduled to attend the orientation session. Those who are not eligible, or decline to participate will be encouraged to quit smoking and given a list of available resources. We will additionally recruit participants at HIV community health centers in Miami. The process here will be the same, where interested participants will be screened for eligibility and scheduled for an orientation session.

Breath carbon monoxide (CO) (for cotinine analysis) will be collected at baseline for participants to confirm their smoking status. The breath sample will be collected with a portable CO monitor (Micro COTM by Micro Direct, Inc.). Cut-offs of < 8 ppm for CO

Clinical Trials Registration #: NCT03999411

Date: 6/29/20

and <10 ng/ml for cotinine will be used to determine smoking status (Benowitz et al 2002).

Participants will be assigned to blocks, based on gender. Then, within each block, participants will be randomly assigned to one of three treatment arms:

- 1. Usual Care (UC)/control: Participants in this group will receive a brief advice to adhere to ART, a brief advice to quit smoking, 6-week supplies of NRT, and self-help materials to quit smoking and adhere to ART.

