- 2. Only smoking cessation intervention (*Crave-to-Quit* app): This intervention is based on the theory of mindfulness-based cognitive therapy (MBCT) for relapse prevention.⁶⁴ The MBCT uses cognitive behavioral therapy methods in collaboration with MT techniques. Cognitive methods focuses on the development of personal coping strategies that target solving problems and changing unhelpful patterns in cognitions (e.g. thoughts, beliefs), behaviors, and emotional regulation.⁶⁵ MT focus on becoming aware of all incoming thoughts and feelings and accepting them, but not attaching or reacting to them.³⁶ This process is known as "Decentering" and aids in disengaging from self-criticism and rumination that can arise when reacting to negative thinking patterns.⁶⁶ Participants in this group will receive the UC for adherence to ART, one in-person orientation sessions, 6-week supplies of NRT, the "*Crave-to-Quit*" app, and two brief follow-up phone calls.

Orientation session. This session will occur 3 weeks before quit date and will last for 90 min. During the session, a research associate will explain the purpose, format, and procedures of the study. Participants will then watch a video that explains the specifics of their respective arm's study activities; there will be a different video for each of the 3 arms. After the video the research associate will go through the written informed consent, have the participant sign, and have the participant complete the baseline assessment. Then, participants will be instructed to download on their phone the "Crave-to-Quit" app and will receive a tutorial explaining the app content and features to troubleshoot any issues, followed by training on how to use the app and to practice MT techniques introduced in the app. Participants will be instructed to start using the app, and the app will assign a quit date within the next 3 weeks. Participants will receive 6 weeks of NRT, and will be instructed to start using the NRT at the quit date. Orientations and collection of consent may be conducted individually or in groups, according to participants' schedules.

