3. The combined intervention (Crave-to-Quit + emocha apps): In addition to the intervention in the second group, participants in this group will be instructed during the *Orientation Session* to download on their phone the *emocha app* and will receive a tutorial explaining the app content and features. The study team will explain to participants that the app will help them in tracking dose-by-dose medication adherence by recording a video for themselves taking their medication. Participants will be instructed to find a private place to take their medication, make sure their face is well lit when recording, have a clear glass of water, state their name, the date, and each medication as they take it, display their medication pills, show medication in the mouth before swallowing, drink water, show open mouth after swallowing, and repeat the same procedure every time they take the medication. During the 3-month trial, our staff will have full access to the app's web portal to navigate and collect information about patients' adherence to ART (pls. see LOS from emocha Mobile Health Inc.).

At the orientation session, participants will complete a baseline assessment consisting of:

- Demographics and HIV history. Age, race/ethnicity, sexual orientation, relationship status, education, employment, income, time since HIV diagnosis, and HIV 1 RNA VL (from medical chart), ART regimen history, time since first starting ART, current ART prescription, 72 VAS for adherence to ART. 61,62
- *Smoking*. Smoking history, past quit attempt, motivation to quit, confidence in quitting, Fagerström test for nicotine dependence, 73 12-item smoking self-efficacy to resist urge to smoke, 74 and 15-item Minnesota nicotine withdrawal scale (i.e., craving, irritability, anxiety, depression). 75

Clinical Trials Registration #: NCT03999411

Date: 6/29/20

Mindfulness skills: The five facet MT questionnaire that measures MT skills related to observing, describing, acting with awareness, non-judging of inner experience, and non-reactivity to inner experience.⁷⁶

• Others. The 10-item Centers for the Epidemiologic Study of Depression (CES-D) scale, 77 social support, 78 quality of life, 79 and alcohol and substance use (ASSIST). 80

Participants will receive \$50 for completing the baseline assessment.

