All participants will receive one in-person follow-up assessment at 3 months after enrollment to assess their smoking status and adherence to ART as well as get information about concomitant smoking and NRT use, use of additional NRT or cessation drugs (e.g., bupropion), and use of other tobacco methods. Breath CO (for cotinine analysis) will be collected at the 3-month follow-up points for participants who report abstinence. The breath sample will be collected with a portable CO monitor (Micro COTM by Micro Direct, Inc.). Cut-offs of 8 ppm for CO and 10 ng/ml for cotinine will be used to determine abstinence (Benowitz et al 2002).

The following will be assessed at the three-month intervention:

- All baseline assessments except demographics.
- *Usability and engagement*. The absolute number of times logged into the apps will be calculated for each user to obtain the mean number of using each app. Two items also will be assessed "self-reported number of completed days for each app," and level of comfort with the app "I am comfortable using the app." Participants in Arms 2 & 3 will also complete The System Usability Scale (SUS) at call 1 & 2 and the 3-month follow-up to evaluate the overall usability of and satisfaction with the app (John Brooke, 1986).
- Acceptability. The acceptability will be assessed by 3 items "How satisfied were you with the intervention?", "How likely are you to recommend this intervention to a friend?" and "How useful was the intervention?"

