- Feasibility. We will monitor rates of recruitment and effort required (e.g. number of staff hours) as well as the number of screenings conducted, proportion eligible, and proportion who agree to enroll. Feasibility of recruitment will be operationalized as an enrollment rate of 70% or higher (an established standard in the RCT literature). We will also record number of rescheduled, cancelled, and missed assessment visits as well as received visits/calls in each treatment arm to inform estimation of staffing needs and retention protocols for a planned efficacy RCT. Other outcomes are rate of attrition (not having a final visit at the end of treatment), rates of several categories of attrition (mortality, withdrawal from the study, transfer to non-study clinics, loss to follow-up without identifiable cause), and response rates to questionnaires (operationalized as 70% or higher), adherence/compliance rates (operationalized as completing at least 70% of the app's module in arm 2 & 3), and time needed to collect and analyze data.

Clinical Trials Registration #: NCT03999411

Date: 6/29/20

• *Smoking Cessation*. Main Smoking cessation outcome is 7-day point-prevalent abstinence (defined as self-report of not smoking in the past 7-days; not even a puff) confirmed by breath CO cotinine level of < 10 ng/ml at the 3-month follow up. Secondary outcome is the reduction in number of cigarettes smoked per day. Relapse is defined as smoking at least once/week on two consecutive weeks. Adherence to ART. >95% adherence to ART (using VAS).

Participants will receive \$50 for completing the three-month assessment.

As an evaluation of the feasibility of the app-based intervention, we will call participants in Arms 2 & 3 once a week for 3 weeks to ask a brief set of questions about their mindfulness practice and use and opinions of the app. Participants will receive \$5 per each of these 3 calls they complete (for a total of up to \$15). From these two arms, we will randomnly select 6 participants that will be asked to complete daily, instead of weekly calls, for a period of 3 weeks; they will receive \$5 per each call for a total of up to \$105 (\$5 per call x 21 calls).

We will use Google Voice to communicate with participants via text for reminders (ex: appointments scheduled, using the apps on schedule, phone call reminders, follow-up reminders). These texts will not mention "HIV", only that it is part of a research study.

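### Participants see the video for their own arm before they sign written consent and complete the self-reported baseline, so entry and baseline answers can depend on the allocation

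*Protocol*

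**What the plan says.** All references are to the protocol.

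- **Allocation** (section 5, Aim 1). After blocking on gender, "within each block, participants will be randomly assigned to one of three treatment arms". No time point is given.
- **Orientation session** (section 5). The associate explains the study, then participants watch a video about the activities of the arm they are in; "there will be a different video for each of the 3 arms". The next step is: "After the video the research associate will go through the written informed consent, have the participant sign, and have the participant complete the baseline assessment". App set-up and training follow.
- **Baseline content** (section 5). The assessment is done at this session and is mostly self-report. It includes "past quit attempt, motivation to quit, confidence in quitting", smoking self-efficacy, withdrawal, mindfulness, depression, social support, quality of life, substance use and the visual analogue scale for ART adherence.
- **Three-month assessment** (section 5). It repeats "All baseline assessments except demographics".
- **Outcomes** (section 5). The main smoking outcome is confirmed 7-day abstinence at 3 months, and the ART outcome is adherence above 95%. "Secondary outcome is the reduction in number of cigarettes smoked per day".
- **Feasibility** (section 5). The team will record "the number of screenings conducted, proportion eligible, and proportion who agree to enroll". The criterion for success in recruiting then reads: "Feasibility of recruitment will be operationalized as an enrollment rate of 70% or higher".
- **Consent** (section 18). Verbal consent is taken by phone before the session. The consent that covers every study activity is the written one, taken at the session.

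**The concern.** Randomisation makes the arms comparable for the people who were allocated. That comparability is secure only if the decision to enter, and the baseline measurements, come before anyone knows the arm. Here both come after.

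Three things are at stake.

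1. **Who enters.** Someone who dislikes the assigned arm can still decline to sign. There are reasons within the plan for this to differ by arm: the combined arm asks people with HIV to film themselves taking every dose, and usual care gives no app to people who must own a smartphone to be eligible. Those who decline leave no questionnaire data. They can be compared with the rest only on registry data, where they came through the registry, or on screening answers.
2. **What they report at baseline.** Expectation or disappointment can shift self-reports. These answers are the starting half of each before-after pair.
3. **What the pilot learns about recruitment.** If enrolment is counted at written consent, the enrolment rate mixes willingness to join a randomised trial with acceptance of a known arm. The planned larger trial needs the first of these on its own.

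**Working it through.** **Order of events.** The protocol states no alpha, power or sample-size derivation that bears on this point, so there is no figure to reproduce. The check is the sequence.

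- The orientation paragraph stands under arm 2, but it says there is one video per arm, and the baseline paragraph places the assessment at the orientation session without limiting it to one arm. The order therefore applies to all three arms.
- A video about a person's own arm cannot be shown until the arm is assigned. So although the time of randomisation is not stated, it must precede the video.
- The resulting sequence is: phone screening and verbal consent → allocation → own-arm video → written consent → baseline → app set-up. Nothing elsewhere in the protocol reverses it.

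**Selective entry (illustration; every rate is assumed).** Take no true effect and two equal halves with quit probabilities of 0.35 and 0.15. Without refusal the rate is 0.5 × 0.35 + 0.5 × 0.15 = 0.250. Let 20% of one arm refuse, all from one half:

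- higher-probability half refuses: (0.3 × 0.35 + 0.5 × 0.15) / 0.8 = 0.225, an error of −2.5 points;
- lower-probability half refuses: (0.5 × 0.35 + 0.3 × 0.15) / 0.8 = 0.275, an error of +2.5 points.

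The sign depends only on who refuses.

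**Enrolment criterion (assumes equal allocation and enrolment counted at written consent).** Pooled acceptance is (UC + 2 × App) / 3, where UC is acceptance in usual care and App is acceptance in each app arm. Setting this to 0.70 gives UC = 2.1 − 2 × App.

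| Both app arms | Usual care | Pooled |
|---|---|---|
| 80% | 50% | 70% |
| 90% | 30% | 70% |
| 100% | 10% | 70% |

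The last row is an arithmetic limit, not an expectation.

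**People allocated but without a questionnaire baseline.** Section 15 allows up to 75 participants. If all 75 are signed consents, the number allocated is 75 / acceptance:

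| Assumed acceptance after the video | Allocated | Not signed |
|---|---|---|
| 90% | 75 / 0.9 = 83.3 | about 8 |
| 80% | 75 / 0.8 = 93.8 | about 19 |
| 70% | 75 / 0.7 = 107.1 | about 32 |

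**Cigarettes per day.** Reduction is baseline minus follow-up. If the baseline is reported at this session, an arm-related shift of x per day moves the between-arm contrast in reduction by x. At the entry minimum of 5 per day, an assumed shift of 1 per day is 1/5 = 20% of baseline. The proportion is smaller for heavier smokers.

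**The case against.** The order of steps is not in dispute; the argument is about how much it matters.

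- **Enrolment may be counted earlier.** Sections 5 and 14 describe people declining at the phone stage, section 18 treats the phone step as agreement to take part, and the feasibility list names agreement to enrol straight after screening and eligibility. On that reading the 70% criterion is settled before any video. This is a fair reading. The protocol does not fix the point, so the feasibility consequence is conditional.
- **Refusal after the video may be rare.** All arms receive six weeks of nicotine replacement, the baseline pays $50 in any arm, and attendees have already agreed by phone and come to the session. These features work against refusal. They do not prevent it, and the protocol gives no acceptance rate in either direction.
- **The illustrated bias is small beside the noise.** With about 25 per arm (equal allocation assumed) and 25% abstinence, the standard error of a two-arm difference is √(2 × 0.25 × 0.75 / 25) = 0.12. A 2.5-point error is then about one fifth of a standard error. That is correct, and it is why this is not a fatal flaw. But imprecision does not excuse an avoidable bias, and the comparison does not touch the baseline self-reports or the recruitment figures.
- **Some smoking information precedes the video.** Eligibility is screened on cigarettes per day. The protocol does not say which value the reduction uses, so exposure of that outcome is also conditional.

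What remains untouched is that written consent and the self-reported baseline follow disclosure of the arm. No later analysis can recover questionnaires from people who declined.

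**Conclusion.** The concern holds. As written, the protocol reveals the allocation before written consent and before the baseline self-reports, and the earlier phone consent does not cure this because it is not the consent that covers the trial's activities.

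The size and direction of the effect on abstinence cannot be derived from the protocol; the figures above show only what assumed refusal rates would do. For the two main efficacy outcomes the exposure is through selective entry. For the reduction in cigarettes per day and the repeated scales it is also through the baseline value. Breath CO and chart viral load are little affected. The feasibility consequence rests on enrolment being counted at written consent, which the protocol leaves open. The time of randomisation is inferred from the arm-specific video. The order should be changed because the change is cheap and removes the problem at its source.

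**What to change.** Reorder the orientation session in section 5:

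1. a common description of all three arms, the same for everyone;
2. written consent;
3. the full baseline assessment, including breath CO;
4. randomisation within gender blocks;
5. the arm-specific video and app set-up, given individually or in single-arm groups.

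State the time of randomisation explicitly, and state that enrolment is counted at signed consent, before allocation. Other definitions of enrolment are possible; what matters is that the point chosen precedes knowledge of the arm. For people already seen under the current order, report by arm how many declined written consent after the video.

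**Cost.** One protocol amendment. The session stays at 90 minutes and no visit is added. The gender-blocked allocation must be available on site during the session. Group sessions must split by arm after baseline, which may need a second room, a second member of staff or staggered videos; individual sessions avoid this.

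### The main cessation outcome is written as a cotinine cut-off although every arm receives NRT; if cotinine is measured, a quitter still on NRT at 3 months would count as not abstinent

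*Protocol*

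**What the plan says.** All of the relevant text is in protocol Section 5 (Procedures Involved), Aim 1.

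- **Outcome definition.** The Smoking Cessation item in the list of 3-month assessments makes the main outcome self-reported 7-day point-prevalence abstinence, "confirmed by breath CO cotinine level of < 10 ng/ml at the 3-month follow up". The value and unit are those the protocol uses elsewhere for cotinine. No CO value appears in this definition.
- **Verification at the visit.** The 3-month follow-up paragraph says: "Cut-offs of 8 ppm for CO and 10 ng/ml for cotinine will be used to determine abstinence". It does not say whether both limits must be met, or which result prevails when they disagree.
- **Specimen.** The same paragraph says: "Breath CO (for cotinine analysis) will be collected at the 3-month follow-up points for participants who report abstinence". The sample is taken with a portable CO monitor, and no other specimen is described.
- **NRT in every arm.** Usual care includes "a brief advice to quit smoking, 6-week supplies of NRT, and self-help materials to quit smoking and adhere to ART". Arm 2 receives "one in-person orientation sessions, 6-week supplies of NRT, the" app and two phone calls. The Arm 3 description begins "In addition to the intervention in the second group, participants in this group will be instructed during the" orientation session to install the second app, so it carries the same NRT supply.
- **NRT at follow-up.** The 3-month visit asks about NRT use alongside smoking, and about "use of additional NRT or cessation drugs (e.g., bupropion"). No sentence connects the answers to how abstinence is scored.

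**The concern.** Cotinine is a metabolite of nicotine and does not show whether the nicotine came from a cigarette or from NRT. A cotinine limit therefore cannot separate a smoker from a non-smoker who is using NRT. The protocol supplies NRT to everyone and asks about continued and additional use at the visit where abstinence is judged, but gives no rule for those who say yes.

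The main smoking outcome is at stake. Someone who has not smoked a puff in 7 days and whose CO is below 8 ppm could fail the written definition solely because of NRT. If NRT use at 3 months differed between arms, part of that difference would appear as a difference in abstinence. The protocol says its findings will inform a larger study, so an unclear definition may also be carried forward.

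**Working it through.** The protocol gives no abstinence rate, power or effect size, so there is no figure of its own to reproduce. The check has three parts.

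**1. What the written rule does to a quitter on NRT.** Take a participant with no smoking for 7 days, CO below 8 ppm, and NRT use that puts cotinine at or above 10 ng/ml.

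- By the CO limit in the follow-up paragraph: abstinent.
- By the cotinine limit in the same paragraph: not abstinent.
- By the main outcome definition, which uses only the 10 ng/ml limit: not abstinent.

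If only breath CO is measured, the second and third lines cannot be evaluated. The participant can then be judged by CO alone, which is not the outcome as written.

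**2. Who could still be on NRT at the visit.** The inputs are a quit date assigned within 3 weeks of orientation, NRT started at the quit date and lasting 6 weeks (all from the Arm 2 description), and a visit 3 months after enrollment, about 13 weeks. I take enrollment to be the orientation session.

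- Quit date at week 0: supply ends at 0 + 6 = week 6, and the gap to the visit is 13 − 6 = 7 weeks.
- Quit date at week 3: supply ends at 3 + 6 = week 9, and the gap is 13 − 9 = 4 weeks.

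For clearance, assume a starting cotinine of 300 ng/ml and a half-life of 16 to 40 hours. The time to fall to 10 ng/ml is half-life × log2(300/10) = half-life × 4.91. That is 79 to 196 hours, or about 3 to 8 days, well inside a 4-week gap. Participants in Arms 2 and 3 who finish on schedule should therefore be clear of supplied nicotine.

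Those exposed are quitters using leftover, late-started or additional NRT. For usual care the arm description states no quit date and no NRT start date, so the timeline cannot be fixed. Anyone starting a 6-week supply after week 13 − 6 = 7 would still be within it at the visit.

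**3. Size, as illustration only.** Assume 25 per arm (75/3, from the stated maximum of 75), truthful self-report, and cotinine at or above 10 ng/ml in every quitter using NRT. Occasional use might not reach that level, so the results are upper limits for the NRT shares used. With u the share of true quitters on NRT at the visit, observed rate = true rate × (1 − u).

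- One person: 5/25 = 20% becomes 4/25 = 16%.
- True rate 20%: u = 10% gives 0.20 × 0.90 = 18%; u = 40% gives 0.20 × 0.60 = 12%.

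For two arms with assumed true rates of 15% (control) and 30% (app), the true difference is 15 points.

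| u control | u app | Observed control | Observed app | Difference (points) |
|---|---|---|---|---|
| 10% | 10% | 13.5% | 27.0% | 13.5 |
| 30% | 30% | 10.5% | 21.0% | 10.5 |
| 50% | 50% | 7.5% | 15.0% | 7.5 |
| 10% | 30% | 13.5% | 21.0% | 7.5 |
| 30% | 10% | 10.5% | 27.0% | 16.5 |

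Equal NRT use shrinks the difference. Unequal use can shrink or inflate it.

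**The case against.** The strongest objection is that the described procedure yields no cotinine result. The only specimen is breath from a CO monitor, which gives no cotinine value in ng/ml. NRT does not raise CO, so on the procedure as described no quitter is misclassified. This stands, and it makes the point conditional. It does not clear the text, because the main outcome is still written as a cotinine limit. If the inconsistency were settled by adding a cotinine assay, the problem would take full effect.

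A reader might infer that the trial will score quitters on NRT as smokers, or that its own NRT supply reverses its main outcome. The documents do not support that. It requires an assay they do not describe, and supply used on schedule in Arms 2 and 3 ends weeks before the visit. A reader might also infer a bias between the arms. All arms receive the same length of supply, and the protocol shows no difference in NRT use at 3 months. The usual-care description gives no start date, which leaves a difference possible but does not establish one. Recording NRT use at the visit also does not show that much of it is expected.

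Two further objections carry less weight. The statistical analysis plan, not seen here, may say how NRT users are classified. The protocol nevertheless fixes the outcome definition itself, and does so with a limit that NRT can breach. It is also true that this is a pilot with no stated power, but potential efficacy is part of its first aim.

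**Conclusion.** The point holds in conditional form. The protocol defines its main cessation outcome by a cotinine limit, lists CO and cotinine limits without saying which governs, gives NRT to all three arms, and has no rule for participants using NRT at the visit.

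- If cotinine is measured and applied as written, true quitters still on leftover, late-started or additional NRT would be scored as not abstinent.
- If only CO is measured, that misclassification does not arise, but the outcome reported is then not the one defined.

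The text needs correcting in either case. The number of participants affected cannot be derived from the protocol. The illustrative sizes rest on assumed abstinence rates, NRT shares and 25 per arm. They show only that at this arm size each misclassified quitter moves an arm's rate by 1/25 = 4 points.

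**What to change.** Amend the 3-month follow-up paragraph and the Smoking Cessation outcome definition in Section 5 together, so that they state one rule:

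1. The main outcome is self-reported 7-day abstinence confirmed by breath CO below the protocol's own 8 ppm cut-off at the 3-month visit.
2. If cotinine is also measured, name the specimen. State that cotinine does not override a CO-confirmed report in anyone reporting current use of NRT or another non-smoked nicotine product, as identified from the item already collected at that visit.

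Both changes are needed. Exempting NRT users alone would leave the outcome unmeasurable, as written, for everyone else.

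The cost is a few sentences, since the CO monitor, the CO cut-off and the NRT question are already in the plan. There are two small downsides. CO reflects recent smoking only, so some light smoking within the 7 days may be missed. If cotinine is also used, the exemption depends on self-reported NRT use.

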The Crave-to-Quit app. The app is comprised of 22 modules for 22 days, 5–15 minutes each, designed to teach MT using audio, video, and animation.⁴⁴ Participants have access to only one new module per day, and subsequent days are locked to prevent skipping ahead (pls. see LOS from [name] from MindSciences). The app teaches three basic formal MT techniques including *Body Scan* (bringing awareness to different parts of the

Clinical Trials Registration #: NCT03999411

Date: 6/29/20

body to foster awareness of body sensations that constitute cravings and affective states), *Loving-Kindness* (repeating phrases such as "may X be happy" to foster acceptance of oneself and others), *Breath Awareness* (paying attention to the breath wherever one feels it most strongly in the body to help retrain the mind away from habitually engaging in self-related thinking toward a more present-centered awareness), and one informal MT RAIN (Recognize, Accept, Investigate, and Note what cravings feel like as they arise/pass away). In RAIN, participants are asked to identify their smoking trigger, rate their craving, and choose between using RAIN to ride out their craving, or completing an audio-guided exercise to 'smoke mindfully' by paying attention to the moment-to-moment experience and bodily sensations of smoking. The app also includes other features such as social support (quit friend sign-ups, the tip of the week), activity feed (to track interaction with the app), and my morning stats (to track smoking).

Two brief follow-up phone calls. The first phone call will occur one day before the quit date to remind participants about their quit date and provide support. The second will occur at the end of treatment (6 weeks after quit date) to review progress, provide support, and schedule the 3-month follow-up visit.

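### Module compliance and log-in figures pool six participants given up to 21 daily evaluation calls with others given 3 weekly calls, which may modestly inflate the feasibility estimates

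*Protocol*

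**What the plan says.** All of this is in Protocol section 5 (Procedures Involved) unless noted.

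- **Purpose of the calls.** They are introduced with the words "As an evaluation of the feasibility of the app-based intervention". They are separate from the two brief follow-up calls listed as part of the Crave-to-Quit intervention.
- **Weekly schedule.** Participants in Arms 2 and 3 are called "once a week for 3 weeks to ask a brief set of questions about their mindfulness practice and use and opinions of the app", at 5 dollars per call and up to 15 dollars.
- **Daily schedule.** From the same arms, "we will randomnly select 6 participants that will be asked to complete daily, instead of weekly calls, for a period of 3 weeks". The payment is 5 dollars "per call x 21 calls", up to 105 dollars. How the six divide between the arms is not fixed.
- **Compliance** (Feasibility bullet). It is "operationalized as completing at least 70% of the app's module in arm 2 & 3".
- **Log-ins** (Usability and engagement bullet). "The absolute number of times logged into the apps will be calculated for each user to obtain the mean number of using each app".
- **App length.** "The app is comprised of 22 modules for 22 days", with one new module released per day.

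Neither measure sets the six apart. Section 2 (Objectives) names feasibility as an aim and says that the findings will inform a larger study.

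**The concern.** The calls are there to observe app use, but a daily question about app use may also prompt it. The six can receive almost one call per module, seven times as many as the other participants in their arms. The protocol itself treats contact as a prompt, since it sends texts reminding participants to use the apps on schedule.

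If daily calls raise use, the pooled compliance rate and mean log-ins describe a mixture of two contact intensities. The more intensive one is not part of the intervention as listed. The larger trial would then be planned on an engagement figure somewhat above what weekly contact produces.

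**Working it through.** **Inputs from the protocol.** Six participants on daily calls; 3 weeks of calls; 5 dollars per call; 22 modules in 22 days; a 70% module criterion; up to 75 participants (section 15); three arms.

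**Assumptions.** The allocation ratio is not stated. With 1:1:1 allocation and 75 enrolled, Arms 2 and 3 hold n = 50. The protocol gives no expected compliance, so p (compliance on weekly calls) and d (compliance among the six) are shown over a range.

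**Stated figures.** 3 × 7 = 21 calls and 21 × 5 = 105 dollars; 3 × 5 = 15 dollars. All reproduce. The ratio of calls is 21/3 = 7. The module criterion is 0.70 × 22 = 15.4, so 16 modules.

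**Effect on pooled compliance.** The pooled rate is p + (6/n)(d − p). With n = 50 the six carry a weight of 6/50 = 0.12.

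| Assumption | Calculation | Pooled rate | Shift |
|---|---|---|---|
| Daily calls add 20 points, any p up to 0.80 | 0.12 × 0.20 | p + 0.024 | 2.4 points |
| All six comply, p = 0.60 | (6 + 44 × 0.60)/50 | 0.648 | 4.8 points |
| All six comply, p = 0.66 | (6 + 44 × 0.66)/50 | 0.701 | 4.1 points |

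The last two rows are upper bounds for those values of p.

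**If fewer are enrolled.** At 60 participants n = 40 and the weight is 15%, so a 20-point effect shifts the rate by 3.0 points. At 45 participants n = 30 and the weight is 20%, so the shift is 4.0 points.

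**Within one arm.** If all six fell in one arm of 25, the weight there is 6/25 = 0.24. A 20-point effect gives 0.24 × 0.20 = 4.8 points. If all six comply and p = 0.65, the shift is 0.24 × 0.35 = 8.4 points. A simple random draw of six from 25 + 25 gives a 3:3 split with probability 0.33, and a split of 5:1 or 6:0 with probability 0.19.

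**Log-ins.** These have no ceiling at 100%. If the six logged in twice as often as the others, the mean would rise by 0.12 × (2 − 1) = 12%.

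**Sampling error for comparison.** At p = 0.65 and n = 50 the 95% half-width is 1.96 × √(0.65 × 0.35/50) = 0.132, about 13 points. With n = 44 it is 0.141, about 14 points.

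**The case against.** - **This may belong in the statistical analysis plan.** Who enters a denominator, and whether a subset is tabulated apart, is often settled there, and that document is not at hand. The six will be known to the study, so nothing is lost irreversibly. This lowers the weight of the point. It does not remove it, because the protocol itself creates the subset and defines the measures across all users.
- **The shift is small beside sampling error.** It is 2.4 points under a 20-point effect, against a half-width of about 13. That stands. The shift would, however, be in one direction if prompting works, and it is avoidable at almost no cost.
- **The other participants are prompted too.** They receive paid weekly calls with the same questions, and the protocol provides text reminders. That stands: leaving out the six gives one uniform call schedule, not a prompt-free estimate of the app alone.
- **Timing and direction are not shown.** The protocol does not say when the three weeks of calls begin. Overlap with the 22-day programme is likely from the length and content of the calls, but it is an inference. Payment is for completed calls, not for using the app, so any effect would come through prompting, which is plausible but unproven.

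A reader might go further and infer that the six could carry the pilot over a 70% feasibility mark. The text does not support that. Enrolment and questionnaire response are written as group rates of 70% or higher. The compliance wording reads most naturally as a threshold for each participant, 16 of 22 modules, and no group pass mark is stated.

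**Conclusion.** The point holds as a modest one. As written, the compliance and log-in measures mix two evaluation schedules that differ sevenfold in the number of calls, and only the lighter one applies to most participants. If the calls overlap the app programme and prompt use, pooled compliance is overstated by about 2.4 points for a 20-point effect among the six. The overstatement is at most 4 to 5 points if all six comply and compliance in the others is 60% to 66%. These figures assume 50 people in Arms 2 and 3. They grow with lower enrolment, and within one arm if the six fall unevenly.

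What is affected is an estimate for planning the larger trial, not a pass or fail decision. The smoking and ART comparisons give no reason to drop anyone.

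**What to change.** Add a sentence to section 5, or to the analysis plan, saying that module compliance and log-ins will be reported by arm, with and without the six daily-call participants. Take the weekly-call participants' figure as the planning estimate for the larger trial. Define the two groups by the random draw, not by calls completed; because the six are drawn at random, setting them aside then introduces no selection bias. Describe the planning figure as app use with weekly calls and text reminders. Keep all randomised participants, including the six, in the smoking and ART comparisons.

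The cost is a line of wording and a denominator of about 44 instead of about 50 for that estimate, which widens the 95% half-width from about 13 to about 14 points at 65% compliance.
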